## CHAPTER I INTRODUCTION

Low back pain (LBP) is one of the most prevalent musculoskeletal conditions and a leading cause of disability across all age groups (**Cieza et al., 2021; Ferreira et al., 2023**). LBP can be classified as acute (lasting less than 6 weeks), subacute (6–12 weeks), or chronic (more than 12 weeks) (**Foster et al., 2021**). Lumbar spondylosis is a degenerative spinal disorder that primarily affects the lower back. It involves age-related changes such as intervertebral disc degeneration, facet joint osteoarthritis, and osteophytes formation (**Ravindra et al., 2020; Jensen et al., 2021; Skundric et al., 2021**). The incidence and prevalence of lumbar spondylosis increases with age. Radiographic evidence of spondylosis is present in more than 95% of individuals over the age of 65 (**Jensen et al., 2021**). Clinical manifestations often include chronic low back pain, stiffness, reduced spinal mobility (**Schmidt et al., 2020; Adams et al., 2021; Skundric et al., 2021**). Lumbar spondylosis can significantly impair daily function and quality of life. It also contributes to increased healthcare costs, absenteeism from work, reduced productivity and greater demands on health care systems (**Ravindra et al., 2020; Skundric et al., 2021; Chen et al., 2022**).

The clinical manifestations of lumbar spondylosis generally consist of chronic low back pain, stiffness, and limited range of motion of the spine, that severely impact a patient's ability to carry out daily function and their overall quality of life (**Schmidt et al., 2020; Adams et al., 2021; Skundric et al., 2021**). These clinical manifestations result in greater healthcare costs, absenteeism from work and diminished productivity, and increased pressure on the healthcare system (**Ravindra et al., 2020; Skundric et al., 2021; Chen et al., 2022**).

Treatments for lumbar spondylosis may involve pharmacological therapy, physiotherapy, or surgical interventions depending on severity and patient response (**Foster et al., 2021; Skundric et al., 2021; Lin et al., 2022**). Conventional physiotherapy for lumbar spondylosis typically includes modalities such as heat, electrical stimulation, stretching, and core strengthening (**George et al., 2020**). A growing body of evidence supports a more holistic approach that incorporates multi-regional mobility training to address the root causes of dysfunctional movement (**Page et al., 2020; Skundric et al., 2021**).

Exercise therapy, particularly core stabilization training, is an important intervention for patients with low back pain because it focuses on activating the deep stabilizing muscles of the trunk (e.g., transversus abdominis and multifidus), which are valuable for segmental control of the spine (**Saragiotto et al., 2020**). By focusing on strengthening these muscles, exercise therapy increases spinal stability, reduces mechanical loading, and improves postural control (**Hodges et**

**al., 2020; García-López et al., 2023).** The evidence supporting this intervention is abundant; core stabilization training has demonstrated significant reductions in pain intensity, improvement in functional outcomes, and reduction in the risk of recurrence in people with lumbar spondylosis (**Liu et al., 2019; Park & Kim, 2020**). For instance, the meta-analysis conducted by **Liu et al. (2019)** showed effective use of progressive core activation programs in pain and disability scores compared to usual care. Additionally, the research by **García-López et al. (2023)** demonstrated that trunk stabilization training caused significantly decreased pain and disability as well as positively altered trunk muscle activation, demonstrating its core value in restoring functional movement, while managing chronic symptoms.

Recently, the importance of thoracic spine and hip mobility exercises have been highlighted in treatment of patients with chronic low back pain (**Sueki et al., 2013; Wainner et al., 2021**). Limitation of thoracic spine and hip mobility has been associated with altered load distribution and increased mechanical stress on the lumbar vertebrae (**Liebenson et al., 2020; Rose et al., 2020; Schmidt et al., 2020**). This suggests that interventions addressing only the lumbar region may be insufficient in restoring functional movement patterns and alleviating symptoms in the long term (**McGill, 2016**).

The thoracic spine contributes significantly to global spinal mobility, especially in rotation and extension (**Johnson et al., 2012; Bordini & Zanier, 2021**). Improving thoracic spine mobility has shown promising effects on reducing low back pain, enhancing dynamic trunk control and optimizing breathing patterns (**Cook et al., 2020; Kumar & Singh, 2021; Chen et al., 2022**).

The hip joint provides essential mobility and stability during walking, squatting, and lifting. In individuals with lumbar spondylosis, limited hip mobility; particularly in extension and internal rotation, is often observed. This restriction leads to compensatory lumbar hyperextension or rotation, contributing to increased mechanical strain on the lumbar spine (**Lewis et al., 2017; Thompson et al., 2021**). Mobility exercises that restore hip joint range, reduce muscle tightness and improve pelvic control can positively influence lumbar biomechanics and reduce pain perception (**Wilson & Clarke, 2023; Martinez-Calderon et al., 2020**).

While previous research has indicated strong effectiveness of core stabilization, thoracic mobility, and hip mobility exercises focused on lumbar conditions, the specific associated benefits of adding these interventions compared one-to-one has not been examined; generally, we observe a void in two specific comparative studies of the two combined approaches (adding thoracic mobility exercises to core stabilization and adding hip mobility exercises to core

stability) with lumbar spondylosis treatment (**Radwan et al., 2024; Skundric et al., 2024**). Therefore, it is not known if treating stiffness in the thoracic region, or restrictions in the hip joint, combined with a core stability program, produces more favorable outcomes in terms of pain relief, functional improvements, and biomechanical changes with regard to lumbar spondylosis. According to author knowledge there is lack of researches that compare between addition of thoracic mobility and hip mobility exercises to core stabilization. So this study seeks to fill this gap by comparing which approach to adjunctive treatment is more effective for lumbar spondylosis specifically.

### **Statement of the Problem**

Which modality is superior when combined with core stabilization for treating individuals with lumbar spondylosis in terms of outcomes: thoracic mobility exercises or hip mobility exercises with regard to severity of pain, disability function, range of motion at the lumbar spine (flexion, extension, lateral flexion, and rotation), spinal mobility, quality of life, and fear of movement?

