### **Purpose of the Study**

This study is conducted to determine the effect of addition of thoracic mobility versus hip mobility exercises to core stabilization on pain severity (NPRS-Ar), functional disability (MODI-Ar), lumbar range of motion (BROM), spinal mobility (modified schober test), quality of life (SF-36-Ar) and fear of movement (Tampa-Ar) in treatment of patients with lumbar spondylosis.

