### **Hypotheses**

1. There will be no significant difference between core stabilization, core stabilization with thoracic mobility exercises, and core stabilization with hip mobility exercises on **pain severity** in participants with lumbar spondylosis.
2. There will be no significant difference between core stabilization, core stabilization with thoracic mobility exercises, and core stabilization with hip mobility exercises on **functional disability** in participants with lumbar spondylosis.
3. There will be no significant difference between core stabilization, core stabilization with thoracic mobility exercises, and core stabilization with hip mobility exercises on **lumbar flexion range of motion** in participants with lumbar spondylosis.
4. There will be no significant difference between core stabilization, core stabilization with thoracic mobility exercises, and core stabilization with hip mobility exercises on **lumbar extension range of motion** in participants with lumbar spondylosis.
5. There will be no significant difference between core stabilization, core stabilization with thoracic mobility exercises, and core stabilization with hip mobility exercises on **lumbar right lateral flexion range of motion** in participants with lumbar spondylosis.
6. There will be no significant difference between core stabilization, core stabilization with thoracic mobility exercises, and core stabilization with hip mobility exercises on **lumbar left lateral flexion range of motion** in participants with lumbar spondylosis.
7. There will be no significant difference between core stabilization, core stabilization with thoracic mobility exercises, and core stabilization with hip mobility exercises on **lumbar right rotation range of motion** in participants with lumbar spondylosis.
8. There will be no significant difference between core stabilization, core stabilization with thoracic mobility exercises, and core stabilization with hip mobility exercises on **lumbar left rotation range of motion** in participants with lumbar spondylosis.

9. There will be no significant difference between core stabilization, core stabilization with thoracic mobility exercises, and core stabilization with hip mobility exercises on **spinal mobility** in participants with lumbar spondylosis.

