### Sample Size Calculation:

A priori power analysis for ANOVA, repeated measures, within-between interactions was used with an effect size of 0.28, alpha level ( $\alpha$ ) = 0.05, and power ( $1-\beta$ ) = 0.95. The estimated sample size required was 54 participants, which was increased to account for potential dropouts as shown in **(Figure 1)**. Thus, the total sample will include 60 participants, randomly allocated into 3 equal groups (n= 20 per group).

Sample size was calculated using G\*Power software version 3.1.9.7, referencing effect size data of pain severity from a recent study studying the effects of thoracic and hip joint mobility exercise with lumbar stabilization exercise on pain and balance **(Choi and Kim, 2023)**.

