**Figure (9): Hip Mobility Exercises. (Demirtas et al., 2023)**

### **Data analysis and statistical design**

Statistical analysis will be performed using SPSS software for Windows, version 25.0 (SPSS, Inc., Chicago, IL) with Alpha level set at 0.05.

- Data will be screened for normality assumption, homogeneity of variance, and presence of extreme scores.
- Descriptive statistics will be calculated for all groups at baseline and after 6 weeks.
- ANOVA, repeated measures, within-between interactions model will be utilized to determine any differences between the mean change scores of groups regarding all outcomes.
- Bonferroni adjusted p-values for every outcome measure to protect against the possibility of type I error.

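### The protocol asks whether thoracic or hip mobility is the better add-on, but no thoracic-versus-hip contrast is stated or sized, so the quoted 0.95 power does not apply to that question

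*Protocol*

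**What the plan says.** Three places in Chapter I of the protocol set a head-to-head question between the two add-ons.

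- The Statement of the Problem puts it as a direct question: "Which modality is superior when combined with core stabilization for treating individuals with lumbar spondylosis in terms of outcomes". The two options that it goes on to name are the thoracic and the hip programme; core stabilization alone is not among them.
- The Purpose of the Study gives the aim as "to determine the effect of addition of thoracic mobility versus hip mobility exercises to core stabilization on pain severity", and then lists the other outcomes.
- The Introduction closes by saying what the trial will add: "So this study seeks to fill this gap by comparing which approach to adjunctive treatment is more effective for lumbar spondylosis specifically".

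The inferential parts are framed differently.

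- Hypotheses: all eleven share one form, "There will be no significant difference between core stabilization, core stabilization with thoracic mobility exercises, and core stabilization with hip mobility exercises on" a given outcome. Each is a null over three groups, one of them the core-only control.
- Sample Size Calculation: the stated method is "A priori power analysis for ANOVA, repeated measures, within-between interactions was used". Its inputs are f = 0.28, a two-sided significance level of 0.05 and a target power of 0.95. This gives 54 patients, raised to 60 (20 per group). The effect size is taken from pain data in a study that the literature review describes as two-group, with thoracic and hip exercise given together in one arm.
- Data analysis and statistical design: the only test named is in the line "ANOVA, repeated measures, within-between interactions model will be utilized to determine any differences between the mean change scores of groups regarding all outcomes". The next bullet applies a Bonferroni adjustment to each outcome measure and does not mention pairwise comparisons.

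**The concern.** An omnibus test over three arms asks whether the arms differ anywhere. The Statement of the Problem asks about one particular difference. Rejecting the omnibus null does not show that one add-on beats the other, because the same result arises when both beat the control by the same amount.

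The power statement has the same gap. A reader of the protocol would take 0.95 as the chance of answering the stated question, but it is the chance of rejecting a different null. The source of the effect size cannot bridge the gap: a study that put both types of exercise in a single arm holds no information on the difference between them.

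At stake is whether the result that the trial is set up to report, and the power quoted for it, speak to the comparison that motivates the trial.

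**Working it through.** Notation: A is core only, B adds thoracic mobility, C adds hip mobility.

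**Inputs from the protocol.** Effect size f = 0.28, alpha 0.05, power 0.95, k = 3 groups, m = 2 measurements (baseline and week 6), N = 54 raised to 60.

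**Assumed.** Pre-post correlation rho = 0.5 and sphericity. The protocol's text does not give rho.

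**Step 1: reproduce the stated sample size.** For the within-between interaction, lambda = f² × N × m / (1 − rho), with df1 = (k − 1)(m − 1) = 2 and df2 = (N − k)(m − 1).

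- N = 54: lambda = 0.0784 × 54 × 2 / 0.5 = 16.93, df 2 and 51, power 0.956. The smallest N is 53, or 54 with equal groups, so the stated figure is reproduced.
- N = 60: lambda = 18.82, df 2 and 57, power 0.973.
- Other correlations do not give 54: rho = 0 needs 102, 0.3 needs 75 and 0.7 needs 33. This is why 0.5 is used below.

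**Step 2: move to the change scale.** With two measurements, the interaction test is a one-way ANOVA on change scores, with f_change = √(lambda / N) = √(18.82 / 60) = 0.56. Here f_change is the standard deviation of the three arm means in units of the SD of change.

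**Step 3: convert f_change = 0.56 into B–C gaps.** The same f fits many patterns of means.

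- Two arms equal and one apart: gap = 0.56 / √(2/9) = 1.19 SD.
- Evenly spaced arms: range = 0.56 × √6 = 1.37 SD, adjacent gap 0.69 SD.

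**Step 4: power for B versus C at 20 per arm.** Noncentral t with pooled error on 57 df and noncentrality gap × √(20/2). For example, 0.686 × √10 = 2.17.

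| Pattern of means | B–C gap (SD of change) | Omnibus power | B–C power, alpha 0.05 | B–C power, alpha 0.05/3 |
|---|---|---|---|---|
| B = C, both differ from A by 1.19 | 0 | 0.973 | 0.05 (type I rate) | 0.017 (type I rate) |
| Evenly spaced, B and C adjacent | 0.69 | 0.973 | 0.57 | 0.39 |
| Only one add-on differs from A | 1.19 | 0.973 | 0.96 | 0.90 |
| B and C at the extremes, A midway | 1.37 | 0.973 | 0.99 | 0.97 |

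A simulation of 100,000 trials of the first pattern at N = 54 gave omnibus rejection in 0.957 and a significant B–C test in 0.051 (0.017 at alpha 0.05/3). This agrees with the formulas.

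**Step 5: detectable B–C difference at 20 per arm, 80% power.** 0.90 SD of change at alpha 0.05, and 1.05 SD at 0.05/3. Baseline adjustment lowers this. At rho = 0.5 the residual SD is √(1 − 0.25) = 0.87 times the SD of change, so 0.90 becomes about 0.90 × 0.87 = 0.78.

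**The case against.** The best defence is that a three-arm design with this model is sound, and that the same fit yields a B–C comparison. Pairwise contrasts are often left to a statistical analysis plan, and the Bonferroni bullet can be read as adjusted pairwise tests within each outcome. The core-only arm also serves a real aim, since the Significance of the Study asks whether treating regions beyond the lumbar spine helps at all, and three-group hypotheses suit that part.

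Much of this stands. The design permits the contrast and needs no change. The Bonferroni bullet may be meant as pairwise testing, though it could equally mean adjustment across outcomes. What it does not repair is that the question, the hypotheses and the sample-size basis are all fixed in this protocol and do not match. Even on the pairwise reading, B versus C has no hypothesis of its own and no power basis.

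Three stronger readings are tempting and are not supported.

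- *The trial has little power for thoracic versus hip.* That holds for some patterns only. In others the power is 0.96 or 0.99, and the protocol gives no expected gap that would choose among them.
- *The question will go unanswered.* The protocol does not say that pairwise comparisons will be omitted.
- *A non-significant result will be reported as equivalence.* The hypotheses are conventional nulls, and nothing in the protocol says that they will be read that way.

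**Conclusion.** The mismatch is real and lies within the protocol. The head-to-head question is posed three times in Chapter I, but the hypotheses, the sizing and the named test are all three-group. The quoted 0.95 power belongs to the omnibus interaction. For thoracic versus hip, the same effect size at 60 patients implies anything from the type I rate to 0.99 (0.97 at alpha 0.05/3), depending on how the means are arranged.

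These figures rest on a pre-post correlation of 0.5, inferred because it reproduces 54, on complete data in 20 patients per arm, and on assumed patterns of means. That the power statement and the question refer to different comparisons depends on none of these.

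**What to change.** 1. Name the baseline-adjusted B-minus-C difference in pain at week 6 as the primary contrast, reported with a 95% confidence interval, and reword the pain hypothesis to match. Pain is the natural choice because the trial was sized on it.
2. Keep B versus A and C versus A as secondary contrasts with a stated multiplicity adjustment, and say plainly what the Bonferroni bullet covers. The choice of adjustment, and whether the omnibus test stays alongside, are matters of preference.
3. In the sample-size section, state that 0.95 is the power of the omnibus test and give the correlation used. Add the B–C difference detectable at 20 per arm: about 0.90 SD of change at 80% power and alpha 0.05, somewhat smaller (about 0.78 if the correlation is 0.5) with baseline adjustment.

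The cost is wording, with the same patients and data. The downside is a less favourable power figure for the primary contrast, and rewording does not itself add precision. If the sponsor wanted 95% power for a stated gap, the trial would have to be sized for it. At an unadjusted alpha of 0.05 on change scores, a gap of 0.69 SD would need 56 per group.

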### **Purpose of the Study**

This study is conducted to determine the effect of addition of thoracic mobility versus hip mobility exercises to core stabilization on pain severity (NPRS-Ar), functional disability (MODI-Ar), lumbar range of motion (BROM), spinal mobility (modified schober test), quality of life (SF-36-Ar) and fear of movement (Tampa-Ar) in treatment of patients with lumbar spondylosis.

### **Significance of the Study**

Lumbar spondylosis is a prevalent degenerative condition affecting 27.2% to 37% of the adult population, with incidence increasing to 80% in individuals over age 40 (**Skundric et al., 2021**). The condition represents a significant contributor to functional disability and healthcare utilization globally (**Ravindra et al., 2020**).

The research explores the principle of regional interdependence by examining thoracic spine and hip mobility contributions to lumbar function (**Kose et al., 2023; Radwan et al., 2024**). Thoracic mobility restrictions may lead to compensatory lumbar hypermobility and increased mechanical stress on lumbar segments (**Radwan et al., 2024; Skundric et al., 2021**). Limited hip mobility, particularly in extension and internal rotation, alters lumbopelvic rhythm and increases lumbar spine stress during functional activities (**Radwan et al., 2024**).

Recent studies about thoracic mobility have shown a specific relationship that exists between improving thoracic function and improving low back pain. According to **Park and Lee (2024)**, patients who participated in thoracic mobility exercise showed greater reductions in pain, greater proprioception and static balance than the group treated with stabilization exercises for low back pain.

**Salah Eldeen et al. (2024)** reported that adding thoracic spine mobilization, to usual physical therapy, had significantly lowered pain levels and better lumbar function in patients with chronic lumbosacral radiculopathy. Additionally, **Kostadinović et al. (2020)** reported greater reductions in pain and disability with closed-chain thoracic mobilization.

Recent studies about hip mobility have shown that addressing limitations in the hips is just as important. **Kim et al. (2021)** reported that improving hip hyperextension reduced the amount of compensatory pelvic tilt in patients with chronic low back pain. **Ferraresi et al. (2022)** reported that improving hip flexor flexibility and strength of the gluteal muscles could reduce mechanical overload on low back pain. **Ceballos-Laita et al. (2023)** reported significant short-term improvements in pain and function with addition of hip-based treatment modalities.

By targeting restrictions beyond the lumbar spine, this integrated approach may enhance outcomes in terms of pain severity, functional disability, lumbar range of motion, spinal mobility, quality of life, and fear of movement in patients with lumbar spondylosis. The current study may provide a more conclusive insight in treatment of patients with lumbar spondylosis.

### **Delimitation**

This study will be delimited to:

**Patients:** 60 patients diagnosed with lumbar spondylosis with age range from 40 to 60 years (**Hodges et al., 2020**).

**Assessment outcomes:** Pain levels in participants were assessed using the Numerical Pain Rating Scale (NPRS-Ar). Functional disability was assessed using the Modified Oswestry Disability Index (MODI-Ar), Lumbar Range of Motion was evaluated using a Back Range of Motion (BROM) device, spinal mobility was assessed with the Modified Schober's test, Health-Related Quality of Life was assessed with the Short Form 36 Health Survey (SF-36-Ar) and fear of movement was assessed using the Tampa scale for Kinesiophobia (Tampa-Ar).

### **Treatment procedures:**

- **Group A (Control Group):** A program of core stabilization exercises including flexibility and strength of core muscle (multifidus and pelvic floor muscles).
- **Group B (First Experimental Group):** A program of core stabilization exercises combined with a program of thoracic mobility exercises including flexibility exercises in all directions of thoracic spine flexion, extension, lateral flexion, and rotation.

- **Group C (Second Experimental Group):** A program of core stabilization exercises combined with a program of hip mobility exercises including flexibility exercises for extensor and internal rotators muscle groups.

